2.1.3 Exploratory Objectives

- Evaluate PFS (by RECIST 1.1 and iRECIST) in each cohort
- Evaluate the association between potential tumor and blood biomarkers and antitumor activity and/or resistance
- Determine the presence and titer of anti-APX005M antibodies (ADA)

2.2 Study Design and Duration

This is a multicenter, open label, Phase 2 study, with 3 parallel cohorts. The aim of the study is to evaluate the efficacy of:

- a) APX005M administered at 2 different schedules to adult subjects with unresectable or metastatic melanoma who have not received prior immunotherapy. Enrolled subjects will be alternately assigned to one of the following 2 cohorts as long as both cohorts are open:
Cohort 1: APX005M administered IV at 0.3 mg/kg every 3 weeks (21-day cycle)

Cohort 2: APX005M administered IV at 0.3 mg/kg every 2 weeks (14-day cycle)

The intent of the alternating cohort assignment is to maintain approximately the same number of treated subjects in each of these 2 cohorts at any given time. Therefore, enrolled subjects assigned to Cohorts 1 or 2 who do not receive APX005M or are not evaluable for tumor response (see below) will be replaced in that cohort before assigning new subjects to the other cohort.

- b) APX005M in combination with stereotactic body radiation therapy (SBRT) in adults with unresectable or metastatic melanoma who have failed approved immunotherapy regimens:

Cohort 3: APX005M administered IV at 0.3 mg/kg in combination with radiation therapy every 2 weeks (14-day cycle) up to 16 weeks followed by APX005M administered IV at 0.3 mg/kg every 2 weeks (14-day cycle).

[figure not shown]
Subjects enrolled in Cohort 3 are required to have a minimum of 3 non-central nervous system (CNS) measurable target lesions as defined in RECIST 1.1 (see [Section 3.2.2](#)). Subjects will receive APX005M combined with SBRT followed by single agent APX005M:

- Four cycles consisting of radiation (one fraction of 800 cGy per cycle delivered to the same target lesion) followed by systemic administration of APX005M every 2 weeks for a total period of 8 weeks.
- Tumor assessment
- Four additional cycles consisting of radiation (one fraction of 800 cGy per cycle delivered to one target lesion different from the one previously irradiated) followed by systemic administration of APX005M every 2 weeks for a total period of 8 weeks.
- Tumor assessment

- Single agent APX005M until any of the criteria in [Section 3.2.6.1](#) are met.

If the first or second radiation therapy targets disappear during radiation treatment, radiation induced toxicity occurs, or radiation dose constraints are met, the remaining radiation fraction scheduled for that particular radiation therapy target can be omitted ([Sections 3.2.2](#) and [3.2.5](#)).

Figure 1: Cohort 3 Study Design

Subjects in all 3 cohorts with unconfirmed PD (iUPD, iRECIST) ([Section 4.3.2](#)) will be permitted to continue treatment as long as

- they meet the criteria in [Section 3.2.6.2](#) and
- they do not have confirmed PD as defined by iRECIST on a repeated tumor assessment 4-8 weeks later.

Subjects that are deemed clinically unstable are not required to have repeat imaging for confirmation of PD.

For every subject the participation in the study consists of 3 periods: Screening Period, Treatment Period and Follow-up Period.

All subjects signing the informed consent form will enter the Screening Period. Procedures and timing of all study related procedures are outlined in [Section 4](#). Treatment period will start with the administration of 1st dose of APX005M ± SBRT and will continue for up to 12 months or until criteria in [Section 3.2.6.1](#) are met.

For the first 2 treatment cycles, subjects will be observed for at least 4 hours following the infusion of APX005M and will return for safety evaluations on Day 2 (24 hours post infusion) and Day 8 (168 hours post infusion). In subsequent cycles, the 4-hour post-infusion observation period and any intracycle safety visits should be scheduled as clinically indicated.

Tumor responses will be evaluated approximately every 8 weeks following the first dose of APX005M. Subjects that discontinue treatment before the first scheduled on-study tumor assessment (8 weeks following the first dose of APX005M) should have the tumor response evaluated at the end of treatment visit. Subjects that are non-evaluable for tumor response will be replaced.

Subjects consenting to collection of tumor biopsies for tumor biomarkers must have a primary or metastatic lesion that can be biopsied without interfering with subsequent tumor assessments.

Subjects who discontinue APX005M will enter the Follow-up Period unless treatment discontinuation is due to withdrawal of consent for all study procedures, initiation of any anticancer therapy, subject lost to follow-up, death, or study termination by Apexigen.

2.2.1 Study Population

2.2.1.1 Inclusion Criteria

- 1) Histologically or cytologically confirmed unresectable or metastatic melanoma
- 2) Subjects with BRAF activating mutation must have received a BRAF inhibitor and/or MEK inhibitor regimen prior to study entry
- 3) Signed written informed consent approved by the relevant local ethics committee(s)
- 4) Male or female ≥ 18 years old at time of consent
- 5) Measurable disease by RECIST 1.1
 - a. For Cohort 3 only, subjects must have at least 3 measurable non-CNS target lesions
- 6) ECOG performance status of 0 or 1
- 7) Resolution of all disease or prior treatment-related toxicities to Grade ≤ 1 , with the exception of alopecia, Grade 2 neuropathy and laboratory abnormalities (parameters below apply). If subject received major surgery or radiation therapy of >30 Gy, they must have recovered from the toxicity and/or complications from the intervention
- 8) Adequate organ function within 14 days prior to first dose of investigational therapy(ies):
 - a. WBC $\geq 2 \times 10^9/L$ in absence of growth factor support
 - b. ANC $\geq 1.0 \times 10^9/L$ in absence of growth factor support
 - c. Platelet count $\geq 100 \times 10^9/L$
 - d. Hemoglobin $\geq 9 \text{ g/dL}$
 - e. Serum creatinine $\leq 1.5 \text{ mg/dL}$
 - f. Calculated (using the formula of local laboratory) or measured creatinine clearance $\geq 60 \text{ mL/min}$

- g. AST and ALT $\leq 2.5 \times$ ULN
- h. Total bilirubin $\leq 1.5 \times$ ULN, or direct bilirubin \leq ULN for subjects with total bilirubin levels $> 1.5 \times$ ULN
- i. INR or PT $\leq 1.5 \times$ ULN unless subject is receiving anticoagulant therapy as long as PT or PTT is within therapeutic range of intended use of anticoagulants
- j. aPTT $\leq 1.5 \times$ ULN unless subject is receiving anticoagulant therapy as long as PT or PTT is within therapeutic range of intended use of anticoagulants

9) Women of childbearing potential (WOCBP) must have a negative serum pregnancy test within the 7 days prior to first dose of investigational therapy(ies) and a negative urine pregnancy test within the 3 days prior to first dose of investigational therapy(ies), or a negative serum pregnancy test within the 3 days prior to first dose of investigational therapy(ies)

10) Women of childbearing potential must agree to follow instructions for method(s) of contraception for the duration of study treatment and 5 months after the last dose of investigational therapy(ies). Males who are sexually active with WOCBP must agree to follow instructions for method(s) of contraception for the duration of study treatment and 7 months after the last dose of investigational therapy(ies)

11) Available archived or fresh tumor tissue sample for biomarker analysis. Note: For Cohort 3, only available archived tissue is required.

12) For subjects that consent to collection of tumor biopsies at study entry and before the first scheduled tumor assessment, primary or metastatic tumor that can be safely biopsied. Up to 18 subjects (6 subjects within each cohort) should consent to fresh core biopsies.

2.2.1.2 Exclusion Criteria

- 1) Prior Therapy:
 - a. Cohorts 1 and 2 only: Previous exposure to any immunomodulatory agent (such as CTLA-4, PD-1/PD-L1, IDO inhibitors, interferon, CD40 agonist etc.).
 - b. Cohort 3 only: Prior therapy with a CD40 agonist. Any number of prior lines of therapy are eligible. A minimum washout period of 21 days from last line of therapy until investigational therapy(ies) administration should be observed
- 2) Second malignancy (solid or hematologic) within the past 3 years except locally curable cancers that have been apparently cured, such as basal or squamous cell skin cancer, superficial bladder cancer, or carcinoma in situ of the prostate, cervix, or breast
- 3) Active, known, clinically serious infections (\geq Grade 2 according to NCI-CTCAE v4.03) within the 14 days prior to first dose of investigational therapy(ies)
- 4) Use of systemic corticosteroids or other systemic immunosuppressive drugs within 28 days prior to first dose of investigational therapy(ies) (except inhaled corticosteroids)
 - a. The use of physiologic doses of corticosteroids may be approved after consultation with the Apexigen Medical Monitor (or designee)
- 5) Major surgery within 4 weeks prior to first dose of investigational therapy(ies)

- 6) Concurrent treatment with any anticancer agent (except for hormonal therapy) and palliative radiation, unless approved by the Apexigen Medical Monitor (or designee)
- 7) History of allogeneic bone marrow transplantation
- 8) Active, known or suspected autoimmune disease
- 9) Active autoimmune disease that has required systemic treatment in past 2 years (i.e. with use of disease modifying agents, corticosteroids or immunosuppressive drugs). Subjects with Type 1 diabetes mellitus, hypothyroidism only requiring hormone replacement, skin disorders (such as vitiligo, psoriasis, or alopecia) not requiring systemic treatment, or conditions not expected to recur in the absence of an external trigger are permitted to enroll
- 10) History of (non-infectious) pneumonitis that required corticosteroids or current pneumonitis
- 11) History of interstitial lung disease
- 12) History of sensitivity or allergy to mAbs or IgG
- 13) Congestive heart failure (New York Heart Association Class III to IV), symptomatic ischemia, conduction abnormalities uncontrolled by conventional intervention, or myocardial infarction within 6 months prior to the first dose of investigational therapy(ies)
- 14) History of any thromboembolic event within 3 months prior to first dose of investigational therapy(ies) or active coagulopathy
- 15) Known active central nervous system (CNS) metastases and/or carcinomatous meningitis. Subjects with untreated brain metastases ≤ 3 mm that are asymptomatic, do not have significant edema, cause shift, and do not require steroids or anti-seizure medications are eligible after discussion with the Medical Monitor. Lesions of any size in posterior fossa are excluded. Subjects with previously treated brain metastases may participate provided they are stable after treatment (without evidence of progression by imaging for at least 4 weeks prior to the first dose of trial treatment and any neurologic symptoms have returned to baseline), have no evidence of new or enlarging brain metastases, and are not using corticosteroids for at least 7 days prior to trial treatment. This exception does not include carcinomatous meningitis which is excluded regardless of clinical stability
- 16) Known human immunodeficiency virus (HIV), hepatitis B or hepatitis C infection
- 17) Has received a live (attenuated) vaccine within 30 days prior to the first dose of investigational therapy(ies). Seasonal flu vaccines that do not contain live virus and COVID-19 vaccines are permitted (see [Section 3.2.3.4](#))
- 18) Has participated in another clinical trial of an investigational drug (or a medical device) within 30 days of study enrollment
- 19) Pregnant, breastfeeding, or unwilling to practice birth control during participation in the study
- 20) Any clinically significant psychiatric, social, or medical condition that, in the opinion of the Investigator, could increase subject's risk, interfere with protocol adherence, or affect

a subject's ability to give informed consent.

2.2.2 Rationale for APX005M Dose

The APX005M regimens (dose and frequency) for all cohorts have been evaluated in prior studies and determined to be well-tolerated and pharmacodynamically-active. In an ongoing study, the combination of APX005M with local radiation treatment and chemotherapy did not result in excess or synergistic toxicity.

3. STUDY PERIODS

3.1 Screening Period

3.1.1 Informed Consent

All subjects will provide written informed consent prior to any study-related activities. All subjects who sign a consent form will enter the Screening Period and be assigned a unique Subject Identification Number. This number will be used to identify the subject throughout the study and must be used on all study documentation.

Subjects will be reconsented, as appropriate, during the course of the study if the informed consent document is revised. Reconsent should be obtained as soon as practicable (e.g., prior to subsequent study drug exposure) or as directed by the local ethics committee(s).

3.1.2 Subject Enrollment

Investigative sites will submit Subject Eligibility Packets (SEPs) for Apexigen Medical Monitor (or designee) review and approval. SEPs will include study-specific eligibility checklist and redacted/anonymized source documents such as the most recent history and physical, imaging reports, and laboratory reports. The Apexigen Medical Monitor (or designee) will review the subject's medical information to confirm eligibility and approve subject's enrollment in the study. During normal business days, a minimum of 2 business days will be required for the Apexigen Medical Monitor (or designee) to review a subject for enrollment. Additional time may be required when approval is sought during a weekend or holiday.

Consented subjects who do not meet eligibility criteria will be considered screen failures.

Enrolled subjects will be alternately assigned to one of the 2 cohorts as long as both cohorts are open. Enrolled subjects assigned to a certain cohort that do not receive APX005M or are not evaluable for tumor response will be replaced in that cohort before assigning new subjects to the other cohort.

3.2 Treatment Period

Enrolled subjects who do not receive APX005M will be considered to have been withdrawn. The Treatment Period will start with the first administration of investigational therapy(ies) and will continue for up to 12 months or until criteria in [Section 3.2.6.1](#) are met.

3.2.1 APX005M Administration

For Cohorts 1 and 2, APX005M is administered on Day 1 of each 3-week or 2-week treatment cycle. In Cohort 3 APX005M will be administered after each fraction of SBRT during the time of combination treatment.

The APX005M infusion time will be 60 minutes. Sites should make every effort to target infusion timing to be as close to 60 minutes as possible. A window between -5 minutes and +10 minutes is permitted (i.e., infusion time is 55 minutes to 70 minutes).

The Pharmacy Manual contains specific instructions for the preparation of the APX005M infusion and administration of infusion solution.

The APX005M infusion can be interrupted in the case of infusion reaction (see [Section 3.2.3.2](#)). Once symptoms resolve, infusion should be restarted at 50% of the initial infusion rate (e.g., from 100 mL/hr to 50 mL/hr).

All subjects will be discharged from clinic after a clinical evaluation. Subjects should have stable vital signs including: lack of orthostatic hypotension (systolic blood pressure >100 mmHg, or no lower than 10 mm from baseline) without IV hydration (no hydration for at least 2 hours prior to discharge), lack of hypoxia (oxygen saturation >90% without oxygen), temperature <38°C, and heart rate <110 beats/min. After discharge, all subjects should be monitored by a caregiver or by a healthcare professional for 24 hours after the first 2 infusions of APX005M and as clinically indicated thereafter.

APX005M and SBRT may be administered up to 3 days after the scheduled Day 1 of Cycle 2 and beyond in case of medical/surgical events, or logistical reasons not related to study therapy (e.g., elective surgery, unrelated medical events, patient vacation, and/or holidays). Treatment delays related to study therapy are discussed in [Section 3.2.4](#).

Administration of APX005M will continue for up to 12 months or until criteria in [Section 3.2.6.1](#) are met.

3.2.2 Radiation Therapy

All subjects should be evaluated and treated by a local radiation oncologist. All radiation treatment will follow the standard guidelines for a SBRT treatment course. Each radiation therapy target lesion will receive up to a total of 3200 cGy in 4 fractions of 800 cGy, administered on the same day and prior to infusion of APX005M. Fractions will be delivered every 2 weeks with the requirement of a minimum of 4 field 3D conformal planning to meet dose constraints to limit normal tissue toxicity of organs at risk (OAR). The first target lesion and the subsequent target lesion will be identified by the treating investigator based upon considerations of clinical benefit and toxicity risk. The RT target lesions shall not be CNS metastases.

First Radiation Therapy Target: One of 3 or more measurable disease lesions (as defined by RECIST 1.1) will be selected as the first radiation therapy target and will be treated every

2 weeks during the first 8 weeks. The radiation field of the first target shall not overlap with any other target lesions.

Second Radiation Therapy Target: The second target shall be one of the remaining non-irradiated lesions where the radiation field does not overlap with the first radiation target. The radiation field shall not overlap with at least one non-irradiated target lesion.

3.2.2.1 Treatment Technology

Based upon the location and size of tumors, treatment planning will be determined by clinical appropriateness. This protocol requires treatment with photons with minimum nominal energy specification of 6 MV. Intensity modulated radiotherapy (IMRT) is encouraged when dosimetric benefit would reduce risk to OARs and may be implemented with static gantry or volumetric modulated arc therapy (VMAT). Tomotherapy delivery is allowed. Though each individual dose may not require high level of precision requiring high level of technology, immobilization and verification the total dose over the 8 weeks will require close monitoring.

3.2.2.2 Immobilization and Simulation

Immobilization: Proper immobilization is important for this protocol. Subject setup reproducibility must be achieved using appropriate clinical devices. A custom immobilization device (such as Alpha Cradle or Vac-Loc) is suggested to minimize set-up variability. SBRT frame and abdominal compression may be appropriate for thoracic and abdominal treatments to minimize motion.

Simulation Imaging: CT Simulation is required, and the images must be acquired using a CT-simulator with a slice thickness ≤ 3 mm. Care should be taken to use the smallest possible FOV that contains the entire surface of the patient with a 512x512 image matrix. Oral and IV CT contrast is optional depending upon the location of the target lesions. The CT simulation must be performed with the patient in the treatment position.

Typical CT scan limits will vary depending on the site. However, it is recommended that the patient will be imaged at least 10 cm cranial and caudal to the target especially if noncoplanar beams will be used.

3.2.2.3 Definition of Target Volumes and Margins

The volumes are to be defined by planning CT/MRI techniques. The extent of palpable tumors should be determined by physical examination to complement imaging and external markers may be helpful for target delineation on CT scans.

3.2.2.4 Detailed Specification

Gross tumor volume (GTV): This includes the target lesion and any adjacent extent or lymph nodes that are considered part of the target lesion. Assessment of the target lesion CT, PET-CT, MRI, or physical exam.

Clinical target volume (CTV): This includes the GTV and suspected microscopic extension and at-risk excluding bone and muscle. Appropriate expansion shall be determined by the treating radiation oncologist and made appropriate for the target site and risk.

Internal target volume (ITV): For target lesions in regions of motion an ITV may be indicated that will take into consideration motion of the target during certain phases of respiration. An appropriate ITV shall be created using 4DCT scans or breath hold scans as indicated for the motion management strategy.

Planning target volume 3200 (PTV): This will provide a margin around the CTV or ITV if appropriate to compensate for the inter- and intra-fraction uncertainty consequent to daily setup uncertainty. By definition, the PTV will consist of a symmetrical 3-7 mm expansion around the CTV or ITV as defined for by radiation oncologist that is specific to institutional standard for the site. In the event that a PTV extends outside of the skin surface, the clinician should manually trim the PTV contours to be 3 mm inside the outer skin (unless there is direct skin involvement).

3.2.2.4.1 **Definition of Critical Structures**

Because treatment sites may vary throughout the body, the treating radiation oncologist shall define the critical structures for the case. This should be defined by the dose constraints (see Tables 1A and 1B) and the proximity of the treated lesion.

Table 1A: Radiation Dose Constraints - Serial Tissue

Serial Tissue	Vol. (cc)	Vol. Max (Gy)	Max Point Dose (Gy)**	Endpoint (\geq Grade 3)
Optic Pathway	<0.2	19.2	21.2	neuritis
Cochlea	-	-	18	hearing loss
Brainstem (not medulla)	<0.5	20.8	27.2	cranial neuropathy
Spinal Cord and Medulla	<5	30	25.6	myelitis
Cauda Equina	<5	26	28.8	neuritis
Sacral Plexus	<5	26	28.8	neuropathy
Esophagus*	<5	30.4	34	esophagitis
Brachial Plexus	<3	24.8	29.6	neuropathy
Heart/Pericardium	<15	28	33	pericarditis
Great Vessels	<10	32	36	aneurysm
Trachea and Large Bronchus*	<5	32	35	impairment of pulmonary toilet
Bronchus- Smaller Airways	<0.5	28.8	35	stenosis with atelectasis
Rib	<5	32	35	pain or fracture
Skin	<10	32	35	ulceration
Stomach	<5	25	33	ulceration/fistula
Bile Duct	-	-	35	stenosis
Duodenum*	<5	25	33	ulceration
Jejunum/Ileum*	<30	22.4	31.6	enteritis/obstruction

Serial Tissue	Vol. (cc)	Vol. Max (Gy)	Max Point Dose (Gy)**	Endpoint (\geq Grade 3)
Colon*	<20	30.8	35	colitis/fistula
Rectum*	<20	32	35	proctitis/fistula
Ureter	-	-	35	stenosis
Bladder Wall	<15	18.5	35	cystitis/fistula
Penile Bulb	<3	27	-	impotence
Femoral Heads	<10	27	-	necrosis
Renal Hilum/Vascular Trunk	15	21.5	-	malignant hypertension

* avoid circumferential irradiation

** "point" defined as 0.035cc or less

*** or one third of the "native" total organ volume (prior to any resection or volume reducing disease), whichever is greater

Table 1B: Radiation Dose Constraints - Parallel Tissue

Parallel Tissue	Critical Volume (cc)	Critical Volume Dose Max (Gy)	Volumetric Constraint	Endpoint (\geq Grade 3)
Lung (right & left)	1500 cc for males and 950 cc for females***	12	-	basic lung function
Lung (right & left)	-	-	V12.8Gy <37%	pneumonitis
Liver	700***	19.6	-	basic liver function
Renal Cortex (right & left)	200***	1	-	basic renal function

*** or one third of the "native" total organ volume (prior to any resection or volume reducing disease), whichever is greater

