3.2.2.4.2 Planning Technique

A 3D conformal or IMRT planning technique must be used. If not using IMRT, field edges and MLC blocking must be conformal to the PTV. The dose distributions must include corrections for tissue density heterogeneities. Regardless of planning technique, the dose prescription criteria specified shall be prioritized.

Table 1C: Radiation Dose Criteria

Name of Structure	Dosimetric Parameter	Per Protocol	Variation Acceptable
PTV	Dmin (%)	\geq 90	\geq 85
	D100% (%)	\geq 95	\geq 85
	Dmax (%)	\leq 130	\leq 150

Replanning: Because melanoma can respond robustly to radiation and treatments will be every 2 weeks it is possible that the tumor volume will be considerably smaller for subsequent fractions. It is recommended that response be assessed after two fractions for bigger tumors or

tumors where decrease in size can considerably impact OARs and toxicity risk. If there has been a decrease of tumor volume by more than 2-fold then a new plan should be considered.

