### 5.3.8 Study Timelines

Date first subject enrolled: 16-Dec-2019

Date last subject enrolled: 21-Oct-2021

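### Table 1A's spinal cord row is inverted: the <5 cc volume maximum (30 Gy) is 4.4 Gy above the point maximum (25.6 Gy), so the volume limit can never bind

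*Protocol*

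**What the plan says.** Protocol section 3.2.2.4.1 tells the treating radiation oncologist to define critical structures by the constraints in Tables 1A and 1B and by how close they lie to the treated lesion. Section 3.2.2 requires conformal planning "to meet dose constraints to limit normal tissue toxicity of organs at risk". The prescription is up to 32 Gy per target, in four fractions of 8 Gy.

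Table 1A lists, in order, a volume, a maximum dose for that volume, a maximum point dose and a toxicity endpoint. The row for "Spinal Cord and Medulla" reads in full "Spinal Cord and Medulla <5 30 25.6 myelitis". The footnote gives a point as "defined as 0.035cc or less".

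No other part of the protocol restates or corrects the cord limits. SAP section 2.3.4.2 repeats the prescription and the general reference to dose constraints, and gives no organ limits.

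**The concern.** A two-tier constraint for a serial organ normally works like this: a very small volume may reach the higher, point dose, and a larger volume is held to a lower dose. The second tier stops a plan from bringing a long stretch of the organ up to the point maximum. In the cord row the larger volume carries the higher dose, so the second tier does no work.

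The endpoint is Grade 3 or higher myelitis. If a lower volume dose was intended, a plan could meet every entry in the table and still expose more cord to doses just under 25.6 Gy than the source constraint allows, and the table would not show it. At least one of the two printed figures is very probably wrong, and section 3.2.2 requires plans to meet them.

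**Working it through.** **Inputs.** Cord volume limit: under 5 cc at 30 Gy. Cord point limit: 25.6 Gy, point = 0.035 cc or less. Prescription: 4 × 8 = 32 Gy. All other rows are from Table 1A.

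**1. Size of the inversion.** 30 − 25.6 = 4.4 Gy; 30 / 25.6 = 1.17. As shares of the prescription, 25.6 / 32 = 80% and 30 / 32 = 93.75%.

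**2. Why the volume limit cannot bind.** Let V(d) be the cord volume receiving more than d Gy. V cannot increase as d increases. The point limit requires V(25.6) ≤ 0.035 cc. Since 30 > 25.6, V(30) ≤ V(25.6) ≤ 0.035 cc. The volume limit asks only that V(30) be under 5 cc, and 5 / 0.035 ≈ 143. Every plan that meets the point limit therefore meets the volume limit with about a 143-fold margin.

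**3. Is this the table's pattern?** Nineteen rows give both limits. In the other 18 the volume dose is lower than the point dose, by 2.0 Gy (optic pathway) to 16.5 Gy (bladder wall). Their ratios run from 18.5 / 35 = 0.53 (bladder wall) to 32 / 35 = 0.91 (trachea, rib, skin, rectum). Where only a point limit is meant, the table prints a dash for volume (cochlea, bile duct, ureter).

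**4. Which entry looks wrong?** These are the neural rows that give both limits (the grouping is mine, not the table's):

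| Row | Volume (cc) | Volume max (Gy) | Point max (Gy) | Difference (Gy) | Ratio |
|---|---|---|---|---|---|
| Optic pathway | <0.2 | 19.2 | 21.2 | −2.0 | 0.91 |
| Brainstem | <0.5 | 20.8 | 27.2 | −6.4 | 0.76 |
| **Spinal cord and medulla** | **<5** | **30** | **25.6** | **+4.4** | **1.17** |
| Cauda equina | <5 | 26 | 28.8 | −2.8 | 0.90 |
| Sacral plexus | <5 | 26 | 28.8 | −2.8 | 0.90 |
| Brachial plexus | <3 | 24.8 | 29.6 | −4.8 | 0.84 |

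The 30 Gy entry exceeds every other volume limit here (highest 26 Gy) and every other point limit (highest 29.6 Gy). At the same <5 cc it allows the cord 30 − 26 = 4 Gy more than the cauda equina, although the cord's point limit is 28.8 − 25.6 = 3.2 Gy lower. The 25.6 Gy entry lies inside the range of the other neural point limits (21.2 to 29.6 Gy).

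If instead 25.6 were the error, or the two cells were swapped, the true cord point limit would be at least 30 Gy, above that of every other neural row. The pattern points to the 30.

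**5. Illustrative size if 30 is the error.** Assume the cord's volume/point ratio lies within that of the other five neural rows, 0.765 to 0.906. The volume limit would then be 25.6 × 0.765 = 19.6 Gy to 25.6 × 0.906 = 23.2 Gy. A plan that meets the table as printed could exceed it by 25.6 − 23.2 = 2.4 Gy to 25.6 − 19.6 = 6.0 Gy. The two rows at the same <5 cc (ratio 0.903) give 25.6 × 0.903 = 23.1 Gy, a gap of 2.5 Gy. The other three rows use different volumes, so the range shows scale only and is not a proposed limit.

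**The case against.** The strongest reply is that nothing unsafe follows. Both limits can be met together, the stricter one governs, and a plan that meets the whole table keeps the cord at or below 25.6 Gy beyond a point. Three other rows have no volume limit at all. A local radiation oncologist plans each case under standard guidelines. Targets may not be CNS metastases and are chosen with toxicity risk in mind from at least three non-CNS lesions. All of this stands, and it limits the consequence. It does not make the row right: the table uses a dash where no volume limit is meant, and here it prints a figure that cannot operate.

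It can also be said that a digit may have been misread when the text was taken from the PDF. The row has all five entries in line with its neighbours, so a shifted column is unlikely. The page image was not examined, so a misread digit is not excluded.

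A reader might infer more than the documents support:

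- **That the protocol permits nearly 5 cc of cord above 30 Gy.** This requires ignoring the next cell of the same row.
- **That the rule on dropping fractions becomes ambiguous.** Protocol section 2.2 says that if "radiation dose constraints are met, the remaining radiation fraction scheduled for that particular radiation therapy target can be omitted". The row still gives one operative answer, because 25.6 Gy is always reached first.
- **That the inversion causes a conflict with target coverage.** Section 3.2.2.4.2 states: "Regardless of planning technique, the dose prescription criteria specified shall be prioritized". If the Table 1C percentages refer to 32 Gy, the 90% minimum dose is 28.8 Gy, above the cord's 25.6 Gy. It is also above the point limits for optic pathway (21.2), cochlea (18) and brainstem (27.2), and the conflict would remain after the 30 Gy cell was corrected. It is a separate, general question.

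**Conclusion.** The row is wrong as printed. The cord has a working point limit of 25.6 Gy and no working volume limit. That the 30 Gy figure cannot bind follows from the two printed values and the definition of a point, and needs no outside source. That 30 is the faulty cell is an inference from the neighbouring rows. It is the most likely explanation, but the documents do not establish it, and they give no corrected value.

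Severity is moderate. Only Cohort 3 receives radiation (18 planned; replacement of non-evaluable subjects could change the number treated). Within it, only subjects with a target near the spine are exposed. The documents do not give that number, and it may be zero. If 25.6 Gy is itself the error, or the cells are swapped, the printed table is stricter than intended and no subject is put at risk by it. Sample size, endpoints and analysis are not affected.

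Timing matters for the remedy. The SAP records "Date last subject enrolled: 21-Oct-2021", and combination treatment lasts up to 16 weeks (112 days). Without delays, a subject starting on that date would finish radiation around 10 February 2022. For subjects already treated, only a look back at their plans can help.

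**What to change.** 1. Check the cord row against the constraint set from which Table 1A was taken, and against the printed page. Reissue the row with a volume dose below the point dose.
2. Until that is done, state that the 30 Gy entry is not to be used and that 25.6 Gy is the cord maximum for any volume above 0.035 cc. This takes the stricter of the two printed figures without deciding which is wrong. If 30 is the error, the volume limit stays open until the source is checked.
3. Identify any Cohort 3 subject with a target near the spine. From the dose-volume record, confirm that the 25.6 Gy limit was met. Once the corrected volume dose is known, report the cord volume above it. For subjects already treated this is the step that matters.

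The cost is one table row, changed by amendment or clarification letter, and a review of what may be few or no plans. No statistical section needs to change.
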